5.3. SAMPLE SIZE

The calculation performed with Nquery (see 13.1) shows that 136 patients are required (68 per group), which is increased to a total of 140 patients to take account patients lost of follow-up.

5.4. PATIENTS IDENTIFICATION

The included patients will be identified by the patient code consisting of:

- First two letters of the name;
- First letter of the first name.

6. STUDIED PRODUCT

6.1. CIRCAID DESCRIPTION

- Composition: circaid® is a medical device of class 1 risk (CE marking 93/42).

It is composed of non-elastic bands adjustable and repositionable thanks to "Velcro" systems. It can be placed on a bandage, on the skin or on an arm or leg sub-sleeve. In order to make the port more discreet, a sock cover or sleeve cover is provided.

The product is made of "breathe-o-prene", a patented derivative of neoprene; breathable, flexible, anti-odor, antimicrobial. The sleeve is composed of: Nylon, Polyurethane, Lycra and Silver for antibacterial effectiveness. The label is made of satin acetate. It does not contain latex.

This orthosis is intended to accommodate a 5% increase or a 10% decrease in limb circumference.

- Mode of action: it is a system of contention composed of several inelastic strips or straps removable, parallel and overlapping slightly to leave no crease and no space between them. "Velcro" tabs or hook-and-loop fasteners ensure proper initial positioning and readjustment of the system as the limb volume is reduced (arm sleeve). This gives a given pressure by tightening or loosening each band while limiting friction and discomfort.

- Comparative: short stretch strips. These are elastic compression belts with low resting pressure, high working pressure, and staying in place day and night. Extensible, they are 100% cotton, guaranteeing a high skin tolerance. They do not contain latex, phthalates and rosin.

6.2. DESCRIPTION OF THE USE OF THE PRODUCTS

The instructions for use of the product are attached in Annex 9 §16.9.

6.3. PACKAGING AND LABELING OF PRODUCTS UNDER STUDY

6.3.1. Primary conditioning

The devices under study are packaged in cardboard boxes by medi France. Depending on the randomization, patients will receive or not at inclusion a box containing a device circaid®, in addition to other materials of the study.

6.3.2. Labeling

Labeling will comply with European regulations, in French.

On the boxes:

- Name and address of the promoter;
- Protocol number "Study Code";
- Lot No XX;
- Content;
- Expiration date: exp.;
- Legal notice: "Product for clinical trial only" "Use under strict medical supervision (Article R5123 of the Public Health Code)" and "Do not leave within the reach of children".

The labels of the boxes containing the products under study will have a repositionable part to stick on the first sheet of the observation book, mentioning the protocol number and the treatment number.

A label model is presented in Annex 1 §16.1 of the protocol.

6.4. ALLOCATION OF PRODUCTS

The products will be provided to the investigator and handed over to the patients.

The investigator will only dispense products to patients included in this trial.

6.5. EXPEDITION AND STORAGE

6.5.1. Expedition

CEN Gestion will provide the circaid® compression devices and all the materials needed for the study to the investigator.

6.5.2. Storage

The products supplied by the promoter will be kept under the responsibility of the investigator under conditions ensuring their good conservation, at room temperature, in a locked room to which only the authorized personnel will have access.

6.6. PRODUCTS NOT USED

Unused products will not be redistributed by the investigator to other patients. They will be kept under the same conditions as the others and will be subject to on-site accounting.

6.7. ACCOUNTING AND RETURN OF PRODUCTS

The circaid® compression devices will be recovered from patients and will be replaced without charge if the doctor deems it necessary and if the patient wishes.

Unused products and empty packaging will be counted at the end of the study by the investigator and by the clinical research assistant who will proceed to their collection.

In case of recall of the products related to the study (decided by the Health Authorities or the sponsor), the investigator will be immediately informed by the sponsor.

The investigator, in collaboration with the representatives of the sponsor (monitors, ARCs) will then urgently:

- stop delivering the products concerned to the patients;
- inform the patients concerned that they must immediately stop using these products and bring them back.

7. CONCOMITENT TREATMENTS

All drug treatments taken by patients and any modifications during the study are allowed but must be documented. All physical treatments for lymphedema other than those prescribed in the protocol are prohibited and will result in exclusion from the study.

8. EVALUATION CRITERIA

8.1. MAIN EVALUATION CRITERION

The main criterion is the frequency of obtaining a 20% reduction in the volume of lymphedema. The volume of lymphedema is defined as the difference between the volume of the limb with lymphedema and the volume of the contralateral healthy limb. The volumes of the arms are calculated by the formula of the truncated cones from the measurements of the perimeters of the arms staged 5 cm in 5 cm from the wrist to the armpit. This method has shown excellent inter- and intra- observer reproducibility compared to the water displacement method. The main criterion is judged at the end of the initial maintenance phase at the 30th day (JS + 30).

8.2. SECONDARY EVALUATION CRITERIA

The secondary evaluation criteria are:

[figure not shown]
- the socio-demographic characteristics: age, occupation;
- the characteristics of lymphedema: origin, date of onset, stage of edema according to the classification of the international society of lymphology, laterality of edema, volume of the arm with lymphedema, and volume of lymphedema compared to the contralateral arm;
- the PGII and CGII;
- the adherence of patients to the wearing of their maintenance treatment by the adapted Morisky score;
- the patient satisfaction in terms of efficiency and wearing comfort measured on Likert scales in 5 classes;
- the occurrence of adverse events and their imputability to the products under study according to the materiovigilance;
- the quality of life of the patients measured by the IFC Lymph specific questionnaire;
- the opinion of the person on the ease of use of the product during the maintenance phase: need of a third person, applications of pressure, continued use, advice to third parties, comparison with possible previous treatments, ease of use employment;
- the need of nurses or caregivers for the setting up of the decongestive device during the maintenance phase.

9. STUDY COURSE

Following the meeting with CNEDIMTS (HAS), three observation periods were defined with the following products:

- D1 to D5: intensive hospital treatment performed by the night and day wearing of the circaid® compression system versus the night and day wearing of short stretching tapes.
- B. DD (Day of discharge from the hospital) to DD +30: ambulatory initial maintenance phase carried out by the wearing of a compression sleeve on the day associated with the nighttime compression system circaid® versus wearing a compression sleeve on the day associated with a possible treatment at night, as recommended by HAS.
- C. DD + 31 to DD + 90: ambulatory maintenance phase carried out by the wearing of a compression sleeve on the day associated with the nighttime circaid® compression system versus the wearing of a compression sleeve on the day associated with possible treatment at night.

Study design:

The study therefore includes four medical follow-up visits on day 0 (D0), day 5 (D5) (+/- 1 day), day of discharge (DD) + 30 days (+/- 5 days) and DD + 90 days (+/- 10 days), followed by self-questionnaire during the maintenance phase between DD and DD + 90, DD designating the day of discharge from the hospital at the end of the intensive reduction phase.

At D0, the doctor:

- collects the informed written consent of the patient after having duly informed her;
- collects its socio-demographic characteristics: age, occupation;
- collects the characteristics of its lymphedema: origin, date of onset, stage of edema according to the classification of the international society of lymphology, laterality of edema, volume of the arm with lymphedema, and volume of lymphedema compared to contralateral arm;

- collects the quality of life measured by the Lymph IFC specific questionnaire;
- implements decongestive treatment with the product defined by randomization.

At D5 (+/- 1 day), the doctor:

- collects the characteristics of lymphedema: stage of edema according to the classification of the international society of lymphology, volume of the arm with lymphedema, and volume of lymphedema compared to the contralateral arm;
- completes the PGII and CGII;
- records patient satisfaction in terms of efficiency and comfort of wearing measured on Likert scales in 5 classes;
- collects the occurrence of adverse events and their imputability to the products under study according to the materiovigilance;
- collects the quality of life measured by the Lymph IFC specific questionnaire;
- gives the patient a self-questionnaire on which she reports each week who has placed the contention device (herself, spouse, nurse), and the existence of an intolerance to the wearing of it;
- gives the patient, according to the randomization list, the products under study during the maintenance phase;
- provides a nursing prescription for the application of a possible treatment to the patients concerned.

At DD + 30 days (+/- 5 days), the doctor:

- collects the characteristics of lymphedema: stage of edema according to the classification of the international society of lymphology, volume of the arm with lymphedema, and volume of lymphedema compared to the contralateral arm;
- collects the PGII and CGII;
- collects the quality of life measured by the Lymph IFC specific questionnaire;
- records patient satisfaction in terms of efficiency and wearing comfort measured on Likert scales in 5 classes;
- collects the observance of the port during the initial maintenance phase by the adapted Morisky score;
- collects the occurrence of adverse events and their imputability to the products under study according to the materiovigilance;
- retrieves the self-questionnaire from the early maintenance period and gives the patient a self-questionnaire for the maintenance period where she reports on each week who apply the compression device (herself, spouse, nurse), and the existence of an intolerance to the wearing of it;
- provides a nursing prescription for the application of a possible treatment to the patients concerned;
- gives the patient, according to the randomization list, the products under study during the maintenance phase.

At DD + 90 days (+/- 10 days), the doctor:

- collects the characteristics of lymphedema: stage of edema according to the classification of the international society of lymphology, volume of the arm with lymphedema, and volume of lymphedema compared to the contralateral arm;
- collects the PGII and CGII;
- collects the quality of life measured by the Lymph IFC specific questionnaire;

- records patient satisfaction in terms of efficiency and wearing comfort measured on Likert scales in 5 classes;
- collects the observance of the port during the long-term maintenance phase by the adapted Morisky score;
- collects the occurrence of adverse events and their imputability to the products under study according to the materiovigilance;
- collects the need for the use of nurses or carers for the application of the decongestive device;
- collects the opinion of the person on the user-friendliness of the product: need of a third party, applications of pressure, continued use, advice to third parties, comparison with possible previous treatments, ease of use;
- retrieves the self-questionnaire of the maintenance period and the products under study;
- writes a prescription of the products that he thinks necessary for the lymphedema.

10. ADVERSE EVENTS

10.1. ADVERSE EVENTS

10.1.1. Definition

An adverse event is defined by any untoward medical occurrence occurring in a patient biomedical research, that does not necessarily have a causal relationship to the research nor the treatment of this. This also includes the signs, symptoms and intercurrent diseases, that may occur during the study period, whether they are related or not with the test product.

In all cases, the etiology should be sought and identified as soon as possible, and the sponsor of the study warned.

10.1.2. Gradation of adverse events

The medical assessment of intensity of adverse event or intercurrent diseases must be determined by using the following definitions:

- Mild: perception of the sign or symptom, but easily tolerated;
- Moderate: sufficiently annoying to interferes with usual activities of daily living;
- Severe: disability with inability to work or usual activities of daily living interruption.

10.1.3. Collection of adverse events

All adverse events will be actively sought from spontaneous statements of patients as well as in the clinical examinations and interrogations by the investigator at each visit.

All adverse events must be documented on CRF including nature, the date of onset, duration, end date, gravity, the therapeutic consequences and evolutions, and the relationship with test product (in the opinion of the investigator). The investigator will specify if it is or not a serious adverse event.

If the adverse event results in the interruption of the study, the 'End of the study' page at the end of the CRF will be completed by the investigator.

10.2. SERIOUS ADVERSE EVENTS

10.2.1. Definition

A serious adverse event (SAE) is defined as follows: any event or adverse reaction which results in death, is life-threatening, requires patient hospitalization or causes prolongation of existing hospitalization, results in persistent or significant disability/incapacity, is a congenital anomaly/birth defect, regardless of the dose given.

Will also be considered as serious adverse events, other events such as: cancer, overdose, pregnancy and any adverse event or biological abnormality appeared during the study period defined as serious by the study protocol or considered by the investigator as sufficiently important or suggestive of a significant risk, contraindications, adverse reactions or precautions for use.

10.2.3. Serious adverse event follow-up

The investigator must provide a specific medical report or complete the form 'Notification of a serious adverse event' (follow-up) and collect all the results of the performed tests and records of hospitalization. Serious adverse events must be followed and documented until disease stabilization or normalization.

10.2.4. Serious adverse events occurring after the study

Any serious adverse event occurring in a patient, within 30 days after the end of the study, should be reported to the sponsor.

The sponsor must also be notified of any event occurring at any time after the end of the study for the patient likely to be linked to the study treatment, according to the investigator.

11. DATA COLLECTION AND MONITORING

11.1. DATA COLLECTION

All data required by the protocol and collected by the investigator must be present in the observation book. A copy of the results of the examinations will be inserted in the observation book after validation by the investigator.

The notebooks will consist of triplicate document (NCR paper):

- the white sheet (original) is intended for the promoter;
- the green sheet is a working document;
- the yellow sheet (strain) is kept by the investigator.

*** Source data**

The investigator is asked to note all the data in the patient's medical record, including:

- the patient's participation in the study with the study code;
- demographic data (date of birth, name);
- medical and surgical history;
- vital parameters;
- concomitant treatments;
- the side effects;
- the information that the patient benefits from a social security scheme.

These data will be noted in a specific file different from the observation book, which will constitute the source data available at any time by the promoter.

11.2. DATA CONTROL

11.2.1. Direct access to source data

By his participation agreement, the investigator is committed to a strict compliance with the experimental protocol, the "Good Clinical Practices" and the amended law of 20 December 1988. It vouches for the authenticity of the data collected within the framework of the study and accepts the legal provisions authorizing the promoter of the study to set up a control of the quality.

In accordance with Good Clinical Practices, the data will be checked on the investigation site by the Clinical Research Assistant.

The investigator is committed to have the necessary availability to receive the Clinical Research Assistant and to keep at his disposal all the source documents for comparison with the observation booklet.

11.2.2. Monitoring visits

11.2.2.1. Pre-selection / implementation visit

The pre-selection procedure will be carried out in the investigative center, through a contact between the Clinical Research Assistant and the investigator to present the protocol and the material, financial, administrative and regulatory aspects of the study.

The aim of this pre-selection is to present, under confidentiality, the protocol to the investigator and his collaborators, to evaluate the adequacy of the human and material resources necessary for the realization of the study and the experiences of the investigator and his collaborators.

During the implementation visit, the Clinical Research Assistant will ensure the presence in the investigating center of all the material required for the study conduct:

- file of the investigator with:
 - experimental protocol and its annexes:
 - . information and consent form for the patient;
 - . curriculum vitae of the coordinator;
 - . insurance certificate;
 - . favorable opinion of the CPP;
 - signed research agreement;
 - regulatory documents (administrative ...);
- observation books;
- products under study;
- study material.

11.2.2.2. Follow-up / closure visits

The study follow-up visit will enable the Clinical Research Assistant to ensure that consent forms are signed by patients or their legal representatives before inclusion in the study, adherence to the protocol and the conformity of the collected data to data source.

The necessary corrections will be made by the investigator, then will be dated and initialed. The original of the CRF thus validated will be recovered by the Clinical Research Assistant.

The closing visit (done at the end of the study) will allow the recovery of the used products not retained by the patients and not used, the CRF and copies of the consent forms, as well as the verification of the conservation conditions of the data of the study (archiving). If necessary, the sponsor may request deferred corrections from the investigator who will sign them.

12. DATA MANAGEMENT

12.1. DATA ENTRY

A double data entry will be performed using a software meeting the standards enacted by the Good Clinical Practices (Capture System). The "computer notebooks" will be the exact image of the CRF. Computer data files as well as any modifications that will be made to them will be saved and retrievable on demand (audit trail).

12.2. DATA CONTROL

A verification of the data will be done by the Clinical Research Assistant and / or the monitor and / or the data manager on the CRF before entry or on the data listings after entry. This verification of the data will be completed by automated logic checks previously programmed. Requests for data corrections will be edited after comparing the double entry files and performing the consistency tests.

12.3. CODING DATA

The data corresponding to the medical history, intercurrent events and associated treatments will be coded according to the MedDRA and ATC dictionaries. The codings will be validated by a doctor.

12.4. DATA FREEZING

The freezing of the database will take place after integration of the requested corrections to the investigating physician and after the Validation Committee composed of the study methodologist, the coordinating investigator and the representative of the sponsor of the study.

It will be signed by the data manager before the database is transmitted to the Biometrics department.

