4. NATURE OF THE TRIAL

Controlled randomized open label clinical trial on two parallel groups.

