5.2. NON-INCLUSION CRITERIA

Not be included in the study:

- from a medical point of view, the patients:
 - with stage I lymphedema;
 - with lymphedema of multiple locations;
 - having had intensive decongestive treatment in the last 6 months;
 - having a recurrence of cancer or a peripheral arterial disease contraindicating or restraining compression.
- from a legal point of view, the patients:
 - not in a position to give free and informed consent because of an administrative or judicial decision or a pathology that may affect their judgment or a difficulty of linguistic comprehension;
 - currently participating in another clinical trial or in an exclusion period from another clinical trial;
 - who may not adhere to the terms of the protocole.

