13.2. PROTOCOL DEVIATIONS AND ANALYSIS PLAN

All cases of deviations from the protocol will be managed according to CEN Biotech's Standard Operating Procedures.

A detailed statistical analysis plan, based mainly on this paragraph of the study protocol, and in accordance with CEN Biotech statistical procedures, will be developed. This analysis plan will be validated by the Medical Director of medi France.

A data validation plan will first focus on defining a position when considering protocol deviations and thus define the analysis populations (Intent to Treat and Per Protocol). The analysis plan will specifically identify the statistical tests, analysis procedures, treatment of missing data considered, and the primary and secondary endpoints that will be used.

Will be considered as major deviations (patient excluded from per protocol analysis) wrong inclusions (non-compliance with the inclusion criteria and non-inclusion) and the absence of data concerning the main criterion of analysis. All other cases will be considered *a priori* as minor deviations.

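### Nothing in the available text masks arm or outcome when deviations are classified in this open-label trial, and wrong inclusion contains an adherence judgement not limited to information known at entry

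*Combined protocol and SAP*

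**What the plan says.** - **Design (section 4).** "Controlled randomized open label clinical trial on two parallel groups".
- **Freeze (section 12.4).** Freezing follows the investigator's corrections and "the Validation Committee composed of the study methodologist, the coordinating investigator and the representative of the sponsor of the study". The section gives this committee no stated task. On the freeze itself it adds: "It will be signed by the data manager before the database is transmitted to the Biometrics department".
- **Populations (section 13.2).** "A data validation plan will first focus on defining a position when considering protocol deviations and thus define the analysis populations". Deviations are handled under the contract research organisation's procedures, and no one is named as deciding them. On the separate statistical analysis plan: "This analysis plan will be validated by the Medical Director of medi France".
- **Major deviations (section 13.2).** There are two: "wrong inclusions (non-compliance with the inclusion criteria and non-inclusion" criteria), and absence of data on the main criterion. Everything else is minor a priori.
- **The judgement criterion (section 5.2).** One group not to be included is patients "who may not adhere to the terms of the protocole". No definition is given.
- **Handling of wrong inclusions (section 14.13.5).** Each case is discussed with the monitor. The patient leaves the study and is replaced, and the available data are kept for the tolerance analysis. There is no time limit and no masking.
- **Analysis sets (sections 13.3 and 13.4.2).** ITT is everyone who applied the study products at least once; PP is everyone without a major deviation. The primary Chi2 test at DD+30 is not tied to either set.

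**The concern.** Whether a patient counts as a wrong inclusion decides whether she is in the per-protocol set. Most eligibility criteria can be checked against records made at entry. The adherence criterion is a forecast. Under section 9, adherence is recorded by the adapted Morisky score at DD+30 and DD+90, the same visits at which arm volumes are measured. By the time deviations are reviewed, evidence of poor adherence therefore sits beside the outcome, and the arm is known because the trial is open label. The plan does not confine the criterion to what was known at D0.

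At stake is the composition of the per-protocol set and, through section 14.13.5, possibly that of the ITT efficacy set. Because section 13.4.2 names no primary population, a per-protocol result could carry the main claim. The optional interim analysis in section 13.4.4 could also show results before populations are settled.

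**Working it through.** **1. The plan's own figure.** Inputs from section 13.1: 75% v 50% responders, two-sided alpha 0.05, power 80%. With mean rate 0.625:

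n = [1.960 × √(2 × 0.625 × 0.375) + 0.8416 × √(0.75 × 0.25 + 0.50 × 0.50)]² / 0.25² = 57.7, so 58 per group.

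This agrees with the plan. The printed table's 25% v 50% also gives 58. For the loss allowance, 58/0.85 = 68.2, against the stated 68. The point below changes none of these figures.

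**2. Which grounds for exclusion leave discretion.**

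| Ground (13.2) | Basis | Discretion after follow-up |
|---|---|---|
| No data on main criterion | DD+30 volume present or absent | None |
| Wrong inclusion, factual criteria | Stage, volume excess, earlier treatment and similar, at entry | Little |
| Wrong inclusion, adherence criterion (5.2) | Forecast, undefined | Some, if not restricted to D0 information |
| All other deviations | Minor a priori | Unclear: the phrase can mean fixed in advance or provisional |

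**3. Conflict over the ITT set.** Under section 13.3 a wrongly included patient who used a product once belongs to ITT. Under section 14.13.5 she is out, replaced, and her data are kept for tolerance. The plan does not say which governs the efficacy analysis.

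**4. How far one exclusion moves a borderline result.** Uncorrected Chi2, as z = (a/n − c/m) / √[p(1−p)(1/n + 1/m)], where p is the pooled rate. The responder counts are chosen for illustration; the documents give none.

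- 39/58 v 29/58: difference 0.1724, p = 68/116 = 0.5862, SE 0.0915, z = 1.885, p-value 0.059.
- One circaid non-responder excluded, 39/57 v 29/58: z = 2.009, p-value 0.045.
- One control responder excluded, 39/58 v 28/57: z = 1.970, p-value 0.049.
- 38/58 v 29/58: p-value 0.091. Four exclusions, two in each arm (38/56 v 27/56): 0.035.
- At 70 per group (140/2, assuming equal allocation), 46/70 v 35/70: 0.060. One circaid non-responder excluded: 0.046.
- Close to the planned effect, 43/58 v 29/58: p-value 0.007, so significance does not depend on an exclusion.

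**5. Worst case over all possible results.** Assume a true rate of 50% in both arms and k exclusions, each chosen because it helps circaid (k is an assumption). Exact binomial enumeration of the chance of a significant result favouring circaid (nominal 0.025):

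| k | 58 per group | 70 per group |
|---|---|---|
| 0 | 0.025 | 0.026 |
| 1 | 0.037 | 0.032 |
| 2 | 0.039 | 0.038 |
| 3 | 0.057 | 0.054 |
| 5 | 0.084 | 0.076 |

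Three such exclusions among 140 patients roughly double the one-sided error (0.0540/0.0258 = 2.1). One exclusion adds 0.0366 − 0.0254 = 0.011 at 58 per group.

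**The case against.** The case against has real force.

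- **Committee.** A reader might infer that the Validation Committee decides the populations. The documents do not say so: section 12.4 gives it no task and section 13.2 names no decision-maker. Section 14.1, on the Scientific Committee, was not in the text available. The gap is silence on who decides and on masking, not a stated sponsor decision.
- **Entry criterion.** A reader might infer that a poor adherer can be excluded without breaking any rule. Section 5.2 governs entry, so relabelling from later behaviour would misapply it. The weakness is only that the plan sets no explicit bar.
- **Poor response.** A reader might also infer that patients who did badly could be called wrong inclusions. Nothing in sections 5.2 or 13.2 makes a poor volume response an eligibility breach; only adherence gives an opening.
- **Safeguards.** Only two grounds exclude a patient, one of them objective. Freeze is signed before the data go to Biometrics. Settling populations before freeze is sound practice. Section 14.13.5 fits detection during recruitment better than a decision at freeze. The promised analysis and data validation plans may contain masking.
- **Size.** The p-value examples start just above 0.05. At 58 per group, a circaid-favouring p-value between 0.05 and 0.0595 has probability about 3.5% at the design rates and about 0.1% if both rates are 50%. That band is not a ceiling on what one exclusion can do, since step 5 gives 1.1 percentage points at 50% in both arms. Still, the opportunity is uncommon and misuse would be rarer.
- **Primary population.** Naming ITT as primary would reduce the weight of per-protocol exclusions more directly. That is true, but it would not settle the conflict between sections 13.3 and 14.13.5.

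These points narrow the concern. They do not supply a D0 limit or a masked review.

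**Conclusion.** The point holds in a limited form. The available text neither assigns nor masks the classification of deviations in an open-label trial, and one of the two grounds for per-protocol exclusion contains an undefined judgement with no limit to entry information. Section 14.13.5 may extend the effect to ITT efficacy.

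The size depends on how close the result is to 0.05. One exclusion can decide a borderline comparison; near the planned effect it is immaterial. The inflation figures assume a 50% rate in both arms and exclusions chosen entirely in circaid's favour, so they are a worst case. The documents do not allow the frequency of such exclusions to be estimated, and nothing in them suggests that they are intended. This is a modest weakness, worth closing because closing it is cheap.

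**What to change.** 1. **Sections 13.2 and 14.13.5.** State that wrong inclusion is judged only on information recorded at or before D0, and that the adherence criterion may not be invoked from later behaviour. This works even where a reviewer recognises the patient.
2. **Sections 12.4 and 13.2.** Name who classifies deviations. Have the data manager supply listings without arm, product or treatment number and without post-baseline volumes, showing DD+30 volume only as present or absent. Sign each patient's population assignment before arm and outcome are merged.
3. **Sections 13.3 and 14.13.5.** Reconcile the two by keeping randomised patients later found ineligible in the ITT efficacy analysis. This concerns the analysis set only, not the patient's care. Where such a patient has no DD+30 volume, the missing-data rule that section 13.2 leaves to the analysis plan must cover her.

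The cost is a paragraph of text and a masked listing program, with no extra patients or visits; 58 and 68 per group stand. Masking will be partial, because the coordinating investigator may recognise patients of their own centre.
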